## 2 PROTOCOL STATEMENT

### 2.1 COMPLIANCE WITH GOOD CLINICAL PRACTICE

This Clinical Study Protocol is designed to comply with the guideline produced by the International Conference on Harmonisation (ICH) on the topic Good Clinical Practice (GCP) as well as other relevant guidelines issued by ICH, primarily the efficacy guidelines.

## 3 PROTOCOL SYNOPSIS

Name of finished/ investigational product:	Ingenol mebutate gel, 0.015%
Name of active substance:	Ingenol mebutate
Title of trial/ protocol code number:	Risk of Squamous Cell Carcinoma on skin areas treated with Ingenol Mebutate Gel, 0.015% and Imiquimod Cream 5% LP0041-63
Co-ordinating investigator(s):	International-co-ordinating investigator: [name] [name], Germany National co-ordinating investigators will be appointed in each participating country.
Estimated number of trial sites and distribution:	Approximately 17 sites in France, 15 sites in Germany and 16 sites in the United Kingdom
Trial period:	First subject first visit planned Q2 2013 Last subject last visit planned Q2 2018
Main objective(s):	Primary Objective: To compare the cumulative incidence of squamous cell carcinoma (SCC) after treatment with ingenol mebutate gel and imiquimod cream. Secondary Objectives To compare the cumulative incidence of neoplasia and the short-term and 12-month efficacy of ingenol mebutate gel with imiquimod cream.

**Methodology:**

This is a phase 4, multi-centre, randomised, two-arm, open label, active-controlled, parallel group, 36-month trial.

All subjects who qualify for inclusion in this trial are to have 5 to 9 clinically typical, visible and discrete actinic keratosis (AK) lesions (confirmed by histopathology of one of the AKs prior to randomisation) within a contiguous 25 cm^2 treatment area on the face or scalp. This area of skin will be referred to as the 'selected treatment area'. Subjects will be randomised in a 1:1 ratio to the following treatment arms:

- Arm A: Ingenol mebutate gel 0.015% applied daily for 3 consecutive days to the selected treatment area followed by 8 weeks' rest. Retreatment for another 3 consecutive days if the treatment field is not completely cleared of AKs at Week 8
- Arm B: Imiquimod 5% cream applied 3 days per week for 4 weeks to the selected treatment area followed by 4 weeks' rest. Retreatment for 4 weeks if the treatment field is not completely cleared of AKs at Week 8.

Study visits will take place at Screening (Visit 1), during the treatment period on Days 1 and 4, Weeks 2, 4 and 8 (Visits 2 to 6) for initial treatment and, if retreatment is required, on Week 8+3 days and Weeks 10, 12, and 16 (Visits 7 to 10). During the Follow-up period visits will take place at Week 20 and Months 12, 18, 24, 30 and 36 (Visits 11 to 16).

At the Screening (Visit 1) subjects will sign the study-specific consent form in the presence of the (Sub)investigator and subject's eligibility will be checked and the selected treatment area will be identified. A 3-4 mm punch biopsy will be taken of one AK lesion in the

---

selected treatment area for histological confirmation of AK.

**Treatment Period (Day 1 to Week 16)**

At Day 1 (Visit 2), the subject eligibility will be confirmed and subjects will be randomised to treatment with either ingenol mebutate gel or imiquimod cream. The selected treatment area will be marked on the skin and the first dose will be applied under the supervision and management of the trial personnel. Subsequent doses will be applied at home. At the next visits (Day 4 and Weeks 2 and 4; Visits 3 to 5) a clinical assessment of neoplasia in the selected treatment area will be performed. If there is suspicion of SCC, basal cell carcinoma (BCC), or other neoplasia when clinical assessment is performed, a 3-4mm punch biopsy will be taken and trial treatment will be stopped but the subject will remain in the trial. The selected treatment area will be assessed for local skin responses (LSRs) and any adverse events (AEs). At Week 8 (Visit 6), a clinical assessment of the selected treatment area will be performed as for previous visits. An AK count in the selected treatment area will also be conducted.

At Week 8, subjects who are completely cleared in the selected treatment area will continue into the Follow-up Period. Subjects, who are not completely cleared in the selected treatment area will have a second treatment cycle and will attend visits at Week 8+3 days and Weeks 10, 12, and 16 (Visits 7 to 10). The assessments will be the same as during the first treatment cycle. After the second treatment cycle (Week 16) subjects will enter the Follow-up Period.

Until the first visit of the follow-up period (Week 20), no

---

other treatments and procedures are allowed in, and within 5 cm of the selected treatment area. Outside the selected treatment area (up to within 5 cm), procedures such as cryotherapy will be allowed; field therapy (e.g. imiquimod) will not be allowed.

**Follow-up Period (Visits from Week 20 to Month 36).**

Visits will be performed at Week 20 and Months 12, 18, 24, 30 and 36 (Visits 11 to 16), at which a clinical assessment of neoplasia in the selected treatment area will be performed. If there is suspicion of SCC, BCC, or other neoplasia when clinical assessment is performed, a 3-4mm punch biopsy will be taken. An AK count in the selected treatment area will be conducted.

From Week 20 until Month 36 procedures such as cryotherapy will be allowed in, and within 5 cm of the selected treatment area. Further, at the discretion of the Investigator and according to nationally available product and treatment guidelines, the same treatment as originally administered is allowed (imiquimod or ingenol mebutate). Cross-over between imiquimod and ingenol mebutate is not allowed. Investigators will be encouraged to pursue these treatment options where clinically relevant before employing other treatments.

Outside the selected treatment area (up to within 5 cm) all treatments will be allowed, although investigators will be encouraged to avoid cross-over between imiquimod and ingenol mebutate.

**Unscheduled/Early Termination**

Upon completion of the last visit or during the study, an unscheduled visit may be required for any subject with a severe reaction, suspected pregnancy or an unresolved

treatment-related AE or LSR (Local Skin Responses), if deemed clinically significant by the investigator. Only assessments that require follow-up will be conducted if the subject is continuing in the trial. For early termination all trial assessments scheduled should be performed.

**Number of subjects entered:**

A total of 480 subjects will be enrolled in the trial and randomised in a 1:1 ratio to the two treatment groups. With 240 patients in each treatment group an adequate precision of the 3-year incidence rate can be obtained. Assuming a 3-year rate of 1.0%, the upper 95% confidence limit will on average be 2.26%, and assuming a 2.5% rate, the upper 95% confidence limit will on average be 4.48%,

**Main criteria for inclusion:**

1. Following verbal and written information about the trial, subject must provide informed consent documented by signing the Informed Consent Form (ICF) prior to any trial-related procedures
2. Subjects with 5 to 9 clinically typical, visible and discrete AKs within a contiguous 25 cm^2 treatment area on the face or scalp. Actinic keratosis should be confirmed by histopathology of one of the AKs prior to randomisation
3. Subject at least 18 years of age.

**Main criteria for exclusion:**

1. Location of the selected treatment area:
  - on the periorbital skin
  - on the perioral skin/around the nostrils
  - within 5 cm of an incompletely healed wound
  - within 10 cm of a suspected BCC or SCC or other neoplasia
2. Selected treatment area lesions that have atypical clinical appearance (e.g., hypertrophic, hyperkeratotic or cutaneous horn)
3. History of SCC, BCC, malignant melanoma or other neoplasia in the selected treatment area

4. History or evidence of skin conditions other than the trial indication that would interfere with evaluation of the trial medication in the selected treatment area (e.g., eczema, unstable psoriasis, xeroderma pigmentosum)
5. Use of ingenol mebutate and/or imiquimod in and within 5 cm of the selected treatment area within 2 years prior to Screening (Visit 1).

**Investigational product:** Ingenol mebutate gel, 0.015%, supplied in a kit of 3 single use, unit dose tubes for topical application.

**Reference product:** Imiquimod 5% cream supplied in a kit of 12 single use, unit dose sachets for topical application

**Duration of treatment:** Each subject will receive a maximum of 2 treatment cycles during the treatment period (Day 1 to Week 16). The Follow-up period will start at Week 16 and continue until Month 36. Each subject will attend a minimum of 12 visits (16 visits if a second treatment cycle is required).

Planned duration:

- Treatment period: 16 weeks including an Initial Treatment Cycle of 8 weeks and a Second Treatment Cycle of 8 weeks (only given when AKs are observed after completion of the First Treatment Cycle).
- Follow-up Period: up to 32 months (from Week 16 to Month 36)

**Assessments:** Identification of the selected treatment area and dermatologic assessments of the selected treatment area must be performed by a dermatologist (board-certified or equivalent). The same dermatologist should attempt to perform all dermatologic examinations of each individual subject.

#### **Investigator assessment**

##### Identification of the selected treatment area

Identification of the selected treatment area and documen-

tation on a study transparency using a three-point landmark technique (See [Appendix IV](#)).

Biopsy and histological confirmation of one AK lesion prior to randomisation.

#### Clinical assessment of the selected treatment area

Clinical assessment of the selected treatment area. Biopsy if there is suspicion of SCC or other neoplasia. All visits.

#### Local skin responses

At all visits from baseline up to Week 20, assessments of LSRs in the selected treatment area using the LSR Grading Scale (See [Appendix III](#)).

#### AK lesion count

Recording of the number of clinically visible AK lesions identified in the selected treatment area on Day 1, Weeks 8, 16 (if retreated), and 20, and Months 12, 18, 24, 30 and 36.

#### Adverse events

Recording of the adverse events at all visits. Adverse events to be reported during the different phases of the trial are detailed in section [10.7.5.1](#).

#### **Laboratory assessment:**

- Biopsy and histological confirmation of one AK lesion prior to randomisation.
- Biopsy if there is suspicion of SCC or other neoplasia. All visits.

#### **Primary end point/ response criterion:**

Diagnosis of SCC (defined as invasive SCC i.e. excludes SCC in situ) in treatment field across the 3-year trial period.

**Secondary end point/  
response criterion:**

1. Diagnosis of SCC and other neoplasia in the treatment field over a 3-year period.
2. Complete clearance after the last treatment cycle (at Week 8 or 16)
3. Partial (at least 75%) clearance after the last treatment cycle (at Week 8 or 16)
4. Complete clearance at 12 months, defined as no AKs at any time in the selected treatment area at any time from the last treatment cycle at Week 8 or 16 through to Month 12.

**Safety evaluation:**

Incidence of Local Skin Responses (LSRs)  
Incidence of adverse events (AEs)  
Incidence of serious adverse events (SAEs)

**Statistical methods:****Analysis of Primary Endpoint**

The 3-year cumulative incidence will be calculated for each treatment group using methods of survival analysis for estimation of cumulative incidence in the presence of censored time-to-event data. Annual incidence rates will also be presented for each group. The cumulative incidence rates will be presented for the event of SCC as primary endpoint and for SCC and other neoplasia as secondary. No formal test comparing the two arms will be performed. For descriptive purposes, as an additional analysis, the difference in cumulative incidence rates between the two arms will be estimated and presented together with its confidence interval.

**Analysis of Secondary Endpoints**

Complete clearance and partial clearance will be estimated and compared between treatment groups using the Cochran–Mantel–Haenszel test.

**Adverse Events**

The primary analysis will be performed on adverse events

occurring within initial treatment cycle, i.e. within 8 weeks of the start of treatment.

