### 10.10.6.2 Adverse Events

Reporting of adverse events will be based on the Safety Analysis Set.

All adverse events recorded will be reported in listings. The investigator's verbatim term of each adverse event will be mapped to SOC and preferred terms using the current version of the Medical Dictionary for Regulatory Activities (MedDRA) thesaurus.

An overall summary of the number (percentage) of subjects with any treatment emergent adverse events (TEAEs), SAEs, premature discontinuations from treatment or from the trial due to adverse events, treatment related AEs, LSRs, severe AEs (maximum intensity indicated as severe in the CRF) will be presented. The overall and treatment related AE summary will also be presented by trial period of the start date of AEs: until Week 20, from Week 20 until Month 12, Month 12 to 24, Month 24 to 36).

The number and percent of subjects with AEs will be tabulated by body system and preferred term for the above summaries. Within a specific body system or preferred term, the subject will be counted only once if more than one event is reported. Summaries will be presented by decreasing frequency.

Listings will be provided for all subjects with SAEs and study discontinuations due to adverse events.

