7.3.5 Adverse Events

Adverse events (AEs) will be presented as described in the CCTP.

Trial ID: LP0041-63	Date: 28-AUG-2019	Version: Final 1.0 Page 12 of 32
---------------------	--------------------------	-------------------------------------

An AE will be considered treatment emergent if the event emerges during treatment having been absent pre-treatment or worsens relative to the pre-treatment state. This is as defined in ICH E9.

Skin malignancies inside the treatment area are defined using Medical Dictionary for Regulatory Activities (MedDRA) v 15.1 as AEs from the Standardised MedDRA Query (SMQ) *skin malignant tumours*. Skin malignancies inside the treatment area will be presented by PT.

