- Table 2-8 Annual incidence of SCC in the treatment area: per protocol analysis set [[Shell 6](#)]
- Table 2-9 Summary of SCC in the treatment area from baseline to end of trial: safety analysis set [[Shell 7](#)]
- Table 2-10 Summary of SCC in the treatment area from baseline to end of trial: per protocol analysis set [[Shell 7](#)]
- Table 2-11 Annual incidence of SCC and other neoplasia in the treatment area: safety analysis set [[Shell 6](#)]
- Table 2-12 Annual incidence of SCC and other neoplasia in the treatment area: per protocol analysis set [[Shell 6](#)]
- Table 2-13 Incidence of SCC in the treatment area by subgroups: safety analysis set [[Shell 8](#)]
- Table 2-14 Incidence of SCC in the treatment area by subgroups: per protocol analysis set [[Shell 8](#)]
- Table 2-15 Incidence of SCC and other neoplasia in the treatment area by subgroups: safety analysis set [[Shell 8](#)]
- Table 2-16 Incidence of SCC and other neoplasia in the treatment area by subgroups: per protocol analysis set [[Shell 8](#)]
- Table 2-17 Incidence of SCC and other neoplasia in the treatment area from week 20 to month 36: safety analysis set [[Shell 5](#)]

Trial ID: LP0041-63	Date: 28-AUG-2019	Version: Final 1.0 Page 19 of 32
---------------------	--------------------------	-------------------------------------

Table 2-18 Incidence of SCC and other neoplasia in the treatment area from week 20 to month 36: per protocol analysis set [[Shell 5](#)]

Table 2-19 Difference in the incidence of SCC in the treatment area: safety analysis set [[Shell 9](#)]

Table 2-20 Difference in the incidence of SCC in the treatment area: per protocol analysis set [[Shell 9](#)]

Table 2-21 Difference in the incidence of SCC and other neoplasia in the treatment area: safety analysis set [[Shell 9](#)]

Table 2-22 Difference in the incidence of SCC and other neoplasia in the treatment area: per protocol analysis set [[Shell 9](#)]

Adverse events

Table 2-23 Overall summary of adverse events from start of treatment to end of trial: safety analysis set

Table 2-24 Overall summary of adverse events from start of treatment to Week 20: safety analysis set

Table 2-25 Overall summary of adverse events from Week 20 to end of trial: safety analysis set

Table 2-26 Overall summary of adverse events by period: safety analysis set

Table 2-27 Adverse events from start of treatment to Week 20 by SOC: safety analysis set

Table 2-28 Adverse events by SOC: safety analysis set

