Table 2-29 Adverse events from start of treatment to Week 20 by SOC and PT: safety analysis set

Table 2-30 Adverse events from Week 20 to end of trial by SOC and PT: safety analysis set

Table 2-31 Frequent adverse events ($\geq 5\%$ in any treatment group) from start of treatment to Week 20 by SOC and PT: safety analysis set

Table 2-32 Frequent adverse events ($\geq 5\%$ in any treatment group) from Week 20 to end of trial by SOC and PT: safety analysis set

Table 2-33 Adverse events from start of treatment to Week 20 by severity, SOC, and PT: safety analysis set

Table 2-34 Adverse events from Week 20 to end of trial by severity, SOC, and PT: safety analysis set

Table 2-35 Related adverse events from start of treatment to Week 20 by SOC and PT: safety analysis set

Table 2-36 Related adverse events from Week 20 to end of trial by SOC and PT: safety analysis set

Trial ID: LP0041-63	Date: 28-AUG-2019	Version: Final 1.0 Page 20 of 32
---------------------	--------------------------	-------------------------------------

Table 2-37 Related adverse events from start of treatment to Week 20 by severity, SOC, and PT: safety analysis set

Table 2-38 Related adverse events from Week 20 to end of trial by severity, SOC, and PT: safety analysis set

Table 2-39 Related adverse events by period, SOC, and PT: safety analysis set

Table 2-40 Adverse events from start of treatment to Week 20 by causal relationship, SOC, and PT: safety analysis set

Table 2-41 Adverse events from Week 20 to end of trial by causal relationship, SOC, and PT: safety analysis set

Table 2-42 Serious adverse events from start of treatment to Week 20 by SOC and PT: safety analysis set

Table 2-43 Serious adverse events by SOC and PT: safety analysis set

Table 2-44 Serious adverse events from start of treatment to Week 20 by causal relationship, SOC, and PT: safety analysis set

Table 2-45 Serious adverse events from Week 20 to end of trial by causal relationship, SOC, and PT: safety analysis set

Table 2-46 Skin malignancies inside treatment area by PT: safety analysis set

Table 2-47 Skin malignancies outside treatment area by PT: safety analysis set

Table 2-48 Adverse events leading to withdrawal from trial by SOC and PT: safety analysis set

Table 2-49 Adverse events from start of treatment to Week 20 by outcome: safety analysis set

Table 2-50 Adverse events from Week 20 to end of trial by outcome: safety analysis set

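### The synopsis's primary adverse-event analysis (first 8 weeks) has no counterpart in Protocol section 10.10.6.2 or the SAP table list, and the SAP does not declare the change

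*Protocol*

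**What the plan says.** The synopsis, under its statistical methods, fixes the window: "The primary analysis will be performed on adverse events" "occurring within initial treatment cycle, i.e. within 8 weeks of the start of treatment". It is the only place in either document that names a primary window for AEs.

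Protocol section 10.10.6.2, the full statistical text on AEs, does not repeat this. It names no primary window and does not mention Week 8. It asks for the overall and treatment-related summaries by the period in which the AE began: "until Week 20, from Week 20 until Month 12, Month 12 to 24, Month 24 to 36".

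SAP section 7.3.5 adds no window of its own: "Adverse events (AEs) will be presented as described in the CCTP". In practice the windows are set by the table titles in SAP Appendix I. Table 2-24 is typical: "Overall summary of adverse events from start of treatment to Week 20: safety analysis set". Other titles cover the whole trial, such as Table 2-23, "Overall summary of adverse events from start of treatment to end of trial: safety analysis set", or carry no cut-off, such as Table 2-28, "Adverse events by SOC: safety analysis set", and Table 2-43, "Serious adverse events by SOC and PT: safety analysis set".

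SAP section 7.5.6 lists the departures from the protocol: the interim analysis, the per-protocol definition, the analysis set for baseline data, and the reasons for stopping treatment. The AE window is not among them.

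**The concern.** A programmer who follows the SAP table list will not produce the analysis that the synopsis calls primary, and a reader of the report will not be told that it was replaced.

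The two windows answer different questions. Under Protocol section 10.1.1 a second cycle is given only if the field is not cleared at Week 8. Up to that point every subject is planned to have one cycle. After it, the number of cycles depends on response, so a window to Week 20 mixes one-cycle and two-cycle subjects in proportions set by each arm's clearance. The SAP tabulates the number of cycles (Tables 1-19 to 1-21) but splits no AE table by it, so the reader cannot separate the two effects. Protocol section 5.3 says that the face and scalp programme for ingenol mebutate initially focused on one cycle, so a first-cycle summary would be informative.

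Ascertainment also differs after Week 8. Retreated subjects attend Visits 7 to 10 and then Visit 11; cleared subjects go straight to Visit 11. AEs are asked about at each visit.

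**Working it through.** There is no plan figure to reproduce. The only precision figures, in Protocol section 10.3, concern SCC incidence and do not enter here.

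**Step 1: count the AE tables by window.** From the titles in SAP Appendix I, Tables 2-23 to 2-51:

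| Window in the title | Tables | Number |
|---|---|---|
| Start of treatment to Week 20 | 2-24, 27, 29, 31, 33, 35, 37, 40, 42, 44, 49 | 11 |
| Week 20 to end of trial | 2-25, 30, 32, 34, 36, 38, 41, 45, 50 | 9 |
| By period | 2-26, 39 | 2 |
| Whole trial, or no cut-off stated | 2-23, 28, 43, 46, 47, 48, 51 | 7 |
| Week 8 or first cycle | none | 0 |

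The total is 11 + 9 + 2 + 7 = 29. Twenty of the 29 split at Week 20; none stops at Week 8.

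**Step 2: AE enquiries between Week 8 and Week 20.** From the schedule in Protocol section 10.7.1 and its first footnote, a retreated subject has Visits 7, 8, 9, 10 and 11, which is five. A cleared subject has Visit 11 only, which is one. The difference is four visits.

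**Step 3: how far Week 20 incidence could move.** This is an illustration. The documents give neither retreatment rates nor per-cycle AE risks for this trial. Assume that both arms have the same risk q of at least one AE per cycle, that cycles are independent, and that a share r of the arm is retreated. Then

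- incidence in the first cycle = q in both arms, so the difference is 0;
- incidence to Week 20 = (1 − r)q + r[1 − (1 − q)²] = q + r·q(1 − q);
- difference to Week 20 = (r₁ − r₂)·q(1 − q).

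| Assumed r₁ vs r₂ | q = 10% | q = 30% | q = 50% |
|---|---|---|---|
| 50% vs 50% | 0 | 0 | 0 |
| 60% vs 40% | 0.20 × 0.09 = 1.8 points | 0.20 × 0.21 = 4.2 points | 0.20 × 0.25 = 5.0 points |
| 80% vs 30% | 0.50 × 0.09 = 4.5 points | 0.50 × 0.21 = 10.5 points | 0.50 × 0.25 = 12.5 points |

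The arm that is retreated more shows the higher Week 20 incidence although the per-cycle risk is identical. The calculation leaves out any effect of the extra visits.

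**Step 4: where the first-cycle window should close.** Visit 6 is Day 57 ± 3, so it may fall from Day 54 to Day 60. For retreated subjects the first dose of the second cycle is applied at that visit (Protocol section 10.1.3). A plain 8-week cut would therefore take in some second-cycle time for a retreated subject seen early. Closing the window at Visit 6, before any second-cycle dose, avoids this.

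**The case against.** The case for leaving the plan alone has several sound parts.

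- Retreatment follows randomisation and is part of each assigned regimen; Protocol section 8.3 shows that it was deliberate. A Week 20 comparison of treated subjects is a valid comparison of the regimens as used. A reader might infer that it is confounded with efficacy. It is not, for its own question; it only fails to isolate the first cycle.
- Week 20 is a natural boundary, because AE reporting rules change there (Protocol section 10.7.5.1, Tables 2 and 3).
- The AE question covers the time since the last visit, so a cleared subject is asked at Week 20 about the whole interval since Week 8. The four extra visits may affect recall, but no period goes unasked.
- Local skin responses are tabulated by visit (SAP Tables 2-52 to 2-67), so a first-cycle comparison is planned for these. The protocol counts them, with application-site disorders, as the main features of the ingenol mebutate safety profile.
- SAP section 7.3.5 defers to the protocol, and Listing 7-6 will list all AEs. A reader might infer that the 8-week analysis will never be produced. The documents show only that it is absent from the planned table list.

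All of this stands, and it limits what can be claimed. It does not supply the missing analysis. Deferring to the protocol does not help when its synopsis and its section 10.10.6.2 differ, and neither the skin-response tables nor a listing summarises first-cycle AEs by arm.

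**Conclusion.** The plan contradicts itself. The synopsis names a primary AE analysis that section 10.10.6.2 omits, that no table in SAP Appendix I provides, and whose loss SAP section 7.5.6 does not record. The count of 0 in 29 tables rests on the titles alone.

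The practical effect cannot be fixed from the documents. Under the assumptions in the working, Week 20 incidence could differ by 1.8 to 12.5 percentage points with no per-cycle difference; if retreatment rates are equal, the difference is zero.

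Three stronger readings are not supported. A reader might infer that every SAP table uses a Week 20 cut-off, but seven have none and two are by period. A reader might infer that the first 8 weeks compare the arms at equal exposure. They equalise planned cycles and calendar time only: one cycle is 3 applications of ingenol mebutate against 3 × 4 = 12 of imiquimod, and some subjects may stop early or not comply. A reader might also turn 60% against 40% retreatment into 14% more treatment (1.6/1.4 = 1.14 mean cycles). That is a ratio of assumed cycle counts, not a change in any AE estimate.

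The AE tables are descriptive and the SCC endpoint is untouched. This is a reporting gap that should be closed, not a flaw in the main comparison.

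**What to change.** Add to SAP Appendix I, labelled as the primary AE analysis named in the synopsis, an overall AE summary and a table by system organ class and preferred term. Both should cover AEs that start from first application up to Visit 6 (Week 8), before any second-cycle dose. State where the window ends for a subject with no Visit 6. Keep the Week 20 and whole-trial tables as they are. Reconcile Protocol section 10.10.6.2 with the synopsis so that both name the same primary window.

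If the sponsor prefers to drop the 8-week analysis, record that in SAP section 7.5.6 with the reason. This cures the inconsistency, though it leaves first-cycle AEs unsummarised.

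The cost is a few repeat tables with a different date window, using AE start dates that are already collected.
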